7. SELECTION AND WITHDRAWAL OF PATIENTS

Investigators should ensure that all study enrollment criteria have been met at screening. If a patient's status changes (including laboratory results or receipt of additional medical records) after screening but before the first dose of study drug is given such that he no longer meets all eligibility criteria, supportive treatment may be administered, if necessary, so that eligibility criteria can be met and laboratory test(s) may be repeated once, to determine if the patient qualifies for the study. If enrollment criteria are not met after further evaluation, then the patient should be excluded from participation in the study.

7.1. Patient Population

Adult male patients ≥ 18 years of age with histologically confirmed adenocarcinoma of the prostate with metastatic disease are eligible for the study.

Screening for eligible patients will be performed within 28 days before administration of the study drug.

The inclusion and exclusion criteria for enrolling patients in this study are described in the following 2 subsections. If there is a question about the inclusion or exclusion criteria below, the investigator must consult with the appropriate sponsor representative and resolve any issues before enrolling a patient in the study. Waivers are not allowed.

7.2. Patient Inclusion Criteria

Each potential patient must satisfy all of the following criteria to be enrolled in the study:

Part 1 Only

1. Must have received at least 2 prior therapies approved for CRPC; including a prior AR inhibitor (e.g., enzalutamide or apalutamide).

Part 2 Only

1. Must have received enzalutamide or apalutamide.
 - (Note: additional therapies approved for CRPC prior to enzalutamide or apalutamide are allowed).

Parts 1 and 2

1. Histologically confirmed adenocarcinoma of the prostate with metastatic disease.
2. Male ≥ 18 years of age.
3. Eastern Cooperative Oncology Group performance status of 0 or 1.
4. Prior orchiectomy or serum testosterone levels < 50 ng/dL determined within 4 weeks prior to start of study drug.
5. Adequate baseline organ function as defined below:

Hematology	
Hemoglobin	≥9 g/dL (or ≥90 g/L) with or without transfusion
Platelet count	≥75 x 10 ⁹ /L with or without transfusion
Neutrophil count	absolute neutrophil count ≥1.0 x 10 ⁹ /L
Chemistry	
Total bilirubin	≤1.5 times laboratory upper limit of normal (ULN); patients with Gilbert's syndrome can enroll if conjugated bilirubin is within normal limits
Alanine aminotransferase and aspartate aminotransferase	≤2.5 times the ULN
Serum creatinine	<1.5 mg/dL, or a calculated or measured creatinine clearance >50 mL/min/1.73 m ²
Cardiac	
Electrocardiogram QTcF	<450 ms (average of 3 readings approximately 2 minutes apart)

6. Ongoing androgen depletion therapy with a gonadotropin-releasing hormone (GnRH) analog or inhibitor, or orchiectomy (i.e., surgical or medical castration). Note: patients who have not undergone orchiectomy must continue GnRH analog therapy for the duration of this protocol.
7. For patients previously treated with first generation anti-androgens (i.e., flutamide, nilutamide, or bicalutamide), discontinuation of flutamide or nilutamide therapy must occur >4 weeks (>6 weeks for bicalutamide) prior to start of study drug with no evidence of an anti-androgen withdrawal response (i.e., no decline in serum PSA).
8. For patients previously treated with chemotherapy targeted therapy, immunotherapy, or treatment with an investigational anticancer agent, discontinuation must have occurred ≥2 weeks, or after at least 4 half-lives, whichever is longer, prior to study drug administration. For enzalutamide and apalutamide, the washout period will be at least 3 weeks prior to start of study drug with no evidence of an anti-androgen withdrawal response (i.e., no decline in serum PSA).
9. For patients previously treated with other agents approved for the treatment of prostate cancer (5-α reductase inhibitors, estrogens, others), discontinuation of therapy must have occurred ≥4 weeks prior to start of study drug.
10. Palliative radiotherapy (to bone or soft tissue lesions) must be completed >2 weeks prior to start of study drug (exception: palliative radiotherapy for pain may be used any time prior to first dose).
11. For patients receiving bone-loss prevention treatment (e.g., bisphosphonates or denosumab), the patient must be on stable dose ≥4 weeks prior to start of study drug.

12. A man who is sexually active with a woman of childbearing potential must agree to use at least two acceptable methods of birth control, one of which must be highly effective ([Section 2.5.1](#)) during the study and for 120 days after receiving the last dose of study drug. Note: a female condom and a male condom should not be used together as friction between the 2 can result in either product failing. All men must also not donate sperm during the study and for 120 days after receiving the last dose of study drug.
13. Patient must be willing and able to adhere to the prohibitions and restrictions specified in this protocol.
14. Each must sign an informed consent form (ICF) indicating that he understands the purpose of and procedures required for the study and is willing to participate in the study. Consent is to be obtained prior to the initiation of any study-related tests or procedures that are not part of standard-of-care for the patient's disease.
15. Each patient must initially sign a separate *pre-screening* informed consent form authorizing collection of the AR mutation sample(s) for genetic research. Consent must be obtained prior to collection of the first AR mutation sample. Participation in this genetic research is required for participation in the study.

7.3. Patient Exclusion Criteria

Any potential patient who meets any of the following criteria will be excluded from participating in the study:

1. History of seizures.
2. Previously documented or current brain metastases.
3. Untreated spinal cord compression.
4. Known positive test result for human immunodeficiency virus.
5. History of clinically significant cardiovascular disease including, but not limited to:
 - Myocardial infarction or unstable angina within the 6 months prior to the first dose of study drug.
 - Clinically significant cardiac arrhythmia.
 - Uncontrolled (persistent) hypertension: systolic blood pressure >180 mmHg; diastolic blood pressure >100 mmHg.
 - Congestive heart failure (New York Heart Association class III-IV).
 - Use of pacemaker
6. Known active or chronic hepatitis B or hepatitis C as demonstrated by hepatitis B surface antigen positivity and/or anti-hepatitis C virus positivity, respectively. Patients with clinically active or chronic liver disease, including liver cirrhosis of Child-Pugh class C, are also excluded.
7. History of a different malignancy except for the following circumstances: (a) individuals with a history of other malignancies are eligible if they have been disease-free for at least

3 years or are deemed by the investigator to be at low risk for recurrence of that malignancy, (b) individuals with a history of treatment for the following cancers are eligible: non-muscle invasive bladder cancer, basal cell, or squamous cell carcinoma of the skin and resected melanoma in situ.

8. Any serious underlying medical or psychiatric condition (e.g., alcohol or drug abuse), dementia or altered mental status or any issue that would impair the ability of the patient to receive or tolerate the planned treatment, to understand informed consent or that in the opinion of the investigator would contraindicate the patient's participation in the study or that would confound the results of the study.
9. Evidence of active viral, bacterial, or systemic fungal infection requiring systemic treatment within 7 days prior to the first dose of study drug. Patients requiring any systemic antiviral, antifungal, or antibacterial therapy for active infection must have completed treatment no less than 7 days prior to the first dose of study drug.
10. Known allergies, hypersensitivity, or intolerance to TRC253 or its excipients (refer to Investigator's Brochure).
11. Enrollment in another therapeutic study.
12. Major surgery (e.g., requiring general anesthesia) within 3 weeks before screening, or has not fully recovered from prior surgery (i.e., unhealed wound), or surgery planned during the time the patient is expected to participate in the study. Note: patients with planned surgical procedures to be conducted under local anesthesia may participate.
13. Plan to father a child while enrolled in this study or within 90 days after the last dose of study drug.
14. Pre-existing chronic hypokalemia or hypomagnesemia.

7.4. Patient Completion, Discontinuation, or Withdrawal

7.4.1. Completion

A patient will be considered to have completed the study if assessments have been completed through the follow-up visit, or if he experiences an event that precludes continuation of study treatment (death, disease progression, unacceptable toxicity).

7.4.2. Discontinuation of Study Treatment

A patient's study treatment must be discontinued if the investigator believes that for safety reasons or tolerability reasons (e.g., adverse event or disease progression) it is in the best interest of the patient to discontinue study treatment. The follow-up visit will be 28 days (\pm 7 days) after the patient discontinues study drug. Patients who have unresolved study-related toxicities will have extended follow-up.

7.4.3. Patient Withdrawal Criteria

A patient will be withdrawn from the study for any of the following reasons:

1. Lost to follow-up or noncompliant

2. Withdrawal of consent
3. The sponsor terminates the study
4. Disease progression according to PCWG3 criteria ([Appendix 2](#), [Appendix 3](#))
 - a. Patients may continue on study drug if in the opinion of the Investigator, patient is deriving benefit from continuation of therapy. Continuation of therapy must be approved by the Sponsor.
5. Dose delay greater than 21 days
Note: In part 1, only patients who have received >75% of TRC253 doses during the DLT evaluation period will be considered evaluable. Patients who have received \leq 75% of TRC253 doses during the DLT evaluation period due to reasons other than toxicities, such as but not restricted to disease progression, missed appointments, non-compliance, and patient withdrawal, will be considered non-evaluable for DLT and will be replaced with a new patient.
6. Patients with AST or ALT elevations >5X ULN, or who meet Hy's Law criteria, i.e., concurrent elevation of AST or ALT >3X ULN and total bilirubin >2X ULN
7. Grade 4 adverse events
8. Patients who experience QTcF prolongation > 500 ms or > 60 ms change from baseline without electrolyte abnormalities and without response to TRC253 (See [Section 8.5.3](#))

If a patient discontinues study drug and withdraws from the study, the off-study visit assessments should be obtained.

If a patient is lost to follow-up, every reasonable effort must be made by the study-site personnel to contact the patient and determine the reason for discontinuation/withdrawal. The measures taken to follow up must be documented.

Study drug assigned to the withdrawn patient may not be assigned to another patient. Patients who withdraw for reasons other than toxicity will be replaced at the discretion of the sponsor.

If the patient withdraws consent, no further evaluation should be performed and no further attempt should be made to collect additional data. Data and samples that have already been collected will still be used as outlined in this study.

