5. STUDY DESIGN AND RATIONALE

5.1. Overview of Study Design

[figure not shown]
This is a multi-center, first-in-human, open-label, Phase 1/2A dose-escalation study in which eligible patients with metastatic CRPC will receive oral doses of TRC253. The study will be conducted in 2 parts as shown in [Figure 1](#).

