5.1.1. Part 1 (Dose Escalation)

During Part 1 of the study, patients will be assigned sequentially to increasing TRC253 doses. The starting dose of TRC253 is 40 mg once daily in the morning, orally (see [Section 5.4](#) for starting dose justification). TRC253 doses will be escalated in subsequent cohorts after all patients enrolled in a given cohort have completed the 28-day DLT evaluation period. Dose escalation in Part 1 will follow single-patient dose escalation design until initial drug-related toxicity occurs per [Table 4](#). When an initial drug-related toxicity occurs per [Table 4](#) or DLT per [Table 6](#) in a single patient the cohort will be expanded according to 3+3 design rules. Cohorts may be expanded to include additional patients for purposes of collecting additional safety, PK, PD (FDHT-PET), and PSA response data. A single cohort may be expanded to a maximum of twelve patients to help inform selection of a MED, as long as that dose level remains below the MTD (see below).

[figure not shown]
Subsequent dose levels will enroll patients based on 3+3 design, whereby 3 patients will be initially enrolled and treated at each dose level. If one of these 3 patients experiences a dose-limiting toxicity (DLT) during the initial 28-day evaluation period, the dose level will be expanded to 6 patients. The MTD will have been exceeded if $\geq 33\%$ of patients experience DLT at a given dose level. DLT will have occurred when a patient has 1 or more toxicity listed in [Table 6](#) that is at least possibly related to TRC253 during the first 28 days of dosing. Patients who exit the study for reasons other than DLT prior to completion of the 28-day DLT evaluation period will be replaced to ensure an adequate safety assessment in each cohort. Patients who experience DLT who receive less than the prescribed dose of TRC253 due to documented toxicity during the DLT evaluation period will be considered evaluable for dose escalation purposes. At the MTD or MED, up to 12 patients may be enrolled.

Figure 4: Single Patient Dose Escalation Schematic

Abbreviations: DLT=dose-limiting toxicity, MTD=maximum tolerated dose.

Figure 5: 3+3 Dose Escalation Schematic

Abbreviations: DLT=dose-limiting toxicity, MTD=maximum tolerated dose.

Dosing during the study will occur as follows:

- The first cohort will receive the oral TRC253 starting dose of 40 mg daily.

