5.1.2. Part 2 (Dose Expansion)

[figure not shown]
Part 2 will consist of three cohorts of initially up to 15 patients (Cohort 1), up to 30 patients (Cohort 2), and up to 15 patients (Cohort 3) to receive TRC253 at the RP2D of 280 mg. The objective of Part 2 is to gather additional information on the safety, PK and PD characteristics, and the clinical efficacy of TRC253 in a pre-defined population of patients with metastatic CRPC. Patients enrolled into Part 2 will have received prior treatment with enzalutamide or apalutamide. Patients will be centrally screened for the presence of the AR F877L and AR L702H mutations from a plasma sample and enrolled into Cohort 1 (AR F877L positive), Cohort 2 (patients without AR F877L and without sole AR L702H mutations), or Cohort 3 (sole AR L702H mutation positive). Note that Cohort 1 patients may be positive for F877L alone or F877L associated with any other AR mutation.

Cohort 1: metastatic CRPC patients with prior enzalutamide or apalutamide and with evidence of AR F877L mutation will be enrolled at the RP2D of 280 mg (AR F877L mutation positive). Note that Cohort 1 patients may be positive for F877L alone or F877L associated with any other AR mutation.

Cohort 2: metastatic CRPC patients with prior enzalutamide or apalutamide without evidence of AR F877L and sole AR L702H mutations but with a different AR mutation or any other mechanism of acquired resistance will be enrolled at the RP2D of 280 mg (AR F877L and sole AR L702H mutation negative).

Cohort 3: metastatic CRPC patients with prior enzalutamide or apalutamide and with evidence of AR L702H mutation will be enrolled at the RP2D of 280 mg (sole AR L702H mutation positive).

Figure 6: Part 2 Cohorts

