14.1. Analysis Populations

The analysis populations are as follows:

- **Safety population:** This population includes all patients who received at least 1 dose of study drug.
- **DLT evaluable analysis set:** This set is a subset of the safety population. Patients who receive $\geq 75\%$ of planned doses of TRC253 or who had a DLT during the DLT evaluation period will be included in this analysis.
- **PK analysis set:** This set consists of all patients who receive at least 1 dose of study drug and have at least 1 post dose concentration measurement of TRC253. This group will be used for summaries (tables and listings) and listings of derived PK parameters. Note: patients will be removed from the estimation of certain PK parameters on an individual basis due to, for example, missing PK samples such that the PK parameters cannot be appropriately derived. These patients will be identified at the time of the analyses along with their reason for removal.
- **Efficacy analysis set:** This population includes all patients who received at least 1 dose of study drug and underwent a relevant efficacy assessment.

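### Sponsor-discretion replacement reaches progressors in open-label Part 2, and the PSA-response denominator does not guarantee that early failures stay in it

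*Combined protocol and SAP*

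**What the plan says.** **Replacement.** Section 7.4.3 and the Synopsis (Withdrawal Criteria) carry the same sentence: "Patients who withdraw for reasons other than toxicity will be replaced at the discretion of the sponsor". It names no study part, no time window and no condition on whether the patient was dosed. Section 5.1.1 has a separate rule for Part 1 only: "Patients who exit the study for reasons other than DLT prior to completion of the 28-day DLT evaluation period will be replaced".

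**Progression.** Item 4 of the withdrawal list in 7.4.3 is "Disease progression according to PCWG3 criteria", with an exception for patients judged to be benefiting. The note under item 5, which is expressly about Part 1, gives disease progression as an example of a reason other than toxicity. Section 7.4.1, in contrast, treats a patient as having completed the study if follow-up is finished "or if he experiences an event that precludes continuation of study treatment (death, disease progression, unacceptable toxicity").

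**Design and size.** Section 5.1 describes a "first-in-human, open-label, Phase 1/2A dose-escalation study". Section 5.1.2 plans "three cohorts of initially up to 15 patients (Cohort 1), up to 30 patients (Cohort 2), and up to 15 patients (Cohort 3").

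**Analysis.** PSA response at Week 12 is a primary endpoint (4.1). Section 14.3 requires a decline of at least 50%, confirmed by a second PSA at least 4 weeks later. For the efficacy analysis set, section 14.1 says: "This population includes all patients who received at least 1 dose of study drug and underwent a relevant efficacy assessment". Section 14.8 reports percent change in PSA at Week 12, or earlier for patients who stop therapy. Section 14 plans no formal hypothesis test.

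**The concern.** Replacement has a clear purpose in Part 1, where each dose level needs enough patients evaluable for DLT. In Part 2 the main efficacy result is an uncontrolled response proportion in cohorts of 15, 30 and 15. There, a discretionary rule that covers progression, applied open-label with PSA results in view, lets decisions about who is enrolled follow from outcomes.

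That does limited damage if the denominator is fixed. Here it is not. It depends on an undefined relevant assessment, and the plan does not say how to classify a patient who lacks a Week 12 or confirmatory PSA. Nor does it say whether a replaced patient still counts towards his cohort's 15 or 30. An early failure could drop out of the denominator while the man who replaces him enters it. Such losses would be mainly non-responders, so any error would push the reported response rate up.

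**Working it through.** **1. The plan's own figures.** Section 14.2 takes a true PSA response rate of 50% in Cohort 2.
- Exact binomial: P(X ≥ 11 | n = 30, p = 0.5) = 0.9506, which matches the stated 95%.
- Exact (Clopper-Pearson) 95% CI for 15/30: 31.3% to 68.7%, which matches.

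Both figures presuppose a fixed denominator of 30.

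**2. Who could be excluded.** Dates follow from Table 8 and 28-day cycles.

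| Event | Timing |
|---|---|
| First on-treatment PSA | Cycle 2 Day 1 = Day 29 |
| First scheduled scan | Cycle 3 Day 1 = Day 57 (week 8) |
| Week 12 PSA | Cycle 4 Day 1 = Day 85 |
| Earliest confirmation on schedule | Cycle 5 Day 1 = Day 113 (week 16) |
| End of Treatment PSA | 7 days after last dose |

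Two readings of the efficacy set follow.
- *Any post-baseline PSA is relevant.* Only a patient who stops before Day 29 and has no End of Treatment PSA is lost. This group should be small.
- *A Week 12 or confirmatory PSA is relevant.* Any patient who stops before Week 12 (or before confirmation) can be lost, including one with soft-tissue progression on the week 8 scan.

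The text does not choose between them.

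**3. Size if k failures are replaced and excluded.** With x responders among n analysed patients, the reported rate is x/n and the rate over all dosed patients is x/(n + k). The ratio is (n + k)/n. The values of x and k are assumptions, and the CIs are exact.

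| Cohort | Replaced failures excluded | All dosed retained | Ratio |
|---|---|---|---|
| 1 or 3 (n = 15, k = 4) | 4/15 = 26.7% (7.8 to 55.1) | 4/19 = 21.1% (6.1 to 45.6) | 19/15 = 1.27 |
| 2 (n = 30, k = 6) | 8/30 = 26.7% (12.3 to 45.9) | 8/36 = 22.2% (10.1 to 39.2) | 36/30 = 1.20 |

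**4. Range.** Let f be the fraction of all enrolled patients who are failures that are both replaced and excluded. With f = k/(n + k), the apparent rate is p/(1 − f). The range of 10% to 30% for f is an assumption.

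| True p | Apparent rate at f = 10 / 20 / 30% | P(≥ 11 of 30): true, then f = 10 / 20 / 30% |
|---|---|---|
| 20% | 22.2 / 25.0 / 28.6% | 0.03, then 0.05 / 0.11 / 0.22 |
| 30% | 33.3 / 37.5 / 42.9% | 0.27, then 0.42 / 0.61 / 0.81 |
| 50% | 55.6 / 62.5 / 71.4% | 0.95, then 0.99 / 1.00 / 1.00 |

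The count of 11 is only the example in section 14.2. The plan does not make it a decision threshold.

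**5. If everyone is retained.** Take p = 50% and replace 6 failures among 30, with the 6 replacements responding at 50%. The expected result is (15 + 3)/36 = 18/36 = 50% with all retained, and 18/30 = 60% with the 6 excluded. The exclusion creates the bias; replacement alone does not.

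**The case against.** A reader might infer that the replacement sentence itself lets treatment failures be swapped out of the Part 2 cohorts. The documents do not support that.
- No section removes a replaced patient from the analysis; replacement adds patients.
- Section 14.8 reports PSA change for early discontinuers, and 7.4.3 keeps data already collected even when consent is withdrawn.
- Table 8 schedules a PSA at End of Treatment, and 7.4.3 asks for off-study assessments, so a man who leaves before Day 29 should usually have a post-baseline value.
- Progression meeting the protocol's criteria before Day 29 is unlikely on schedule. Appendix 2 says to continue through early PSA rises for at least 12 weeks unless there is other evidence of progression. The first scan is at week 8. Under Appendix 3, new bone lesions on that scan need confirmation on the next, which is scheduled at Cycle 6, after Week 12.
- Section 7.4.1 counts progressors as completers, so it is arguable whether they withdraw at all.
- No test or go/no-go threshold is planned, the cohort sizes are already soft, and the paired intervals above overlap heavily.

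A reader might also see a contradiction between mandatory replacement in 5.1.1 and discretion in 7.4.3. A specific rule for the DLT window beside a general rule is a normal reading, so that point is weak.

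Most of this stands, and it limits the concern. It does not close the gap. Section 14.8 governs the reported percent change and does not set the response denominator. An End of Treatment PSA does not help if relevant means Week 12. The conflict between 7.4.1 and 7.4.3 leaves the question open and does not act as a safeguard.

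**Conclusion.** The concern holds in a limited form. The plan allows replacement of Part 2 progressors with outcomes in view, and it pairs this with a response denominator that depends on an undefined assessment and has no non-responder rule. Together these can inflate the Week 12 PSA response rate; neither the replacement sentence nor the open-label design does so alone.

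The inflation factor is (n + k)/n: 1.27 for 4 excluded failures in a cohort of 15, and 1.20 for 6 in a cohort of 30. These figures assume that the failures are both replaced and excluded. The documents give no count of replacements and do not show that any exclusion took place. If every dosed patient is retained, the bias is negligible and only the cohort size grows. If any post-baseline PSA qualifies, few patients are at risk; if a Week 12 or confirmatory value is required, anyone stopping earlier is.

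The effect is on descriptive estimates only. Section 14 defers detail to a statistical analysis plan, and the text reviewed contains no separate one, so a rule may exist there. The change is still worth making, because it replaces a stated analysis-set rule with a less biased one at little cost.

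**What to change.** 1. In 14.1 and 14.3, define the Part 2 PSA-response denominator as every dosed patient in the cohort, including any who are replaced. Count a patient without a confirmed Week 12 response as a non-responder.
2. In 7.4.3 and the Synopsis, limit discretionary replacement to Part 1 patients non-evaluable for DLT and to Part 2 patients who were never dosed. If wider Part 2 replacement is kept, report the number replaced in each cohort with reasons, and state whether replaced patients count towards the 15, 30 and 15. Once item 1 is in place, a ban on replacing dosed patients is optional.
3. Reconcile 7.4.1, where progression counts as completion, with 7.4.3, where it counts as withdrawal, so that the scope of the replacement sentence is clear.

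The cost is short edits to these sections by amendment and, if replacement is kept, one listing. The reported response rate may be slightly lower. If replacement is restricted, fewer patients in each cohort will reach Week 12; if it is kept, a cohort may exceed its planned size.
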